5. STUDY CONDUCT

5.1 Restrictions during the study

Patients should be fasting (at least 6 hours) before blood sampling for baseline laboratory analysis.

Patients should not donate blood or bone marrow at any time during the study.

Restrictions regarding concomitant medications are described in Section 5.6.

5.2 Patient enrolment and randomisation

The Principal Investigator or delegate will:

1. Obtain signed informed consent from the potential patient before any study specific procedures are performed
2. Determine patient eligibility (see Sections 4.1 and 4.2)

3. Assign (using the Interactive Voice Response System/Interactive Web Response System [IVRS/IWRS], see Section 5.2.1) potential patients a unique enrolment number, beginning with 'E#'
4. Assign enrolled patient a unique randomisation code (patient number) in IVRS/IWRS.

If a patient withdraws from participation in the study, then his/her enrolment/randomisation code cannot be reused. Patients can only be randomised into the study once.

5.2.1 Procedures for randomisation

The randomisation codes will be computer generated by AstraZeneca R&D using the AZ Global Randomisation system (GRand) and loaded into the IVRS/IWRS database. Randomisation codes will be generated in blocks to ensure approximate balance (1:1) between the two treatment arms. Randomisation will be done via IVRS/IWRS at Visit 2. The IVRS/IWRS will allocate randomisation codes sequentially within each centre as patients become eligible for randomisation. Once a block of randomisation codes is exhausted, the next available block will be allocated by the IVRS/IWRS to the centre. For each patient randomised the IVRS/IWRS will provide the investigator with a unique Kit ID number matching the treatment arm assigned to the patient. Following randomisation, the first dose of study medication will be administered to the patient as soon as possible.

At randomisation and every subsequent dispensing visit the patient should always be provided medication with the Kit ID(s) allocated by the IVRS/IWRS. If a patient receives the incorrect randomised treatment at any time during the study, this must be corrected as soon as discovered.

5.3 Procedures for handling patients incorrectly enrolled or randomised

Patients who fail to meet the inclusion/exclusion criteria should not, under any circumstances, be enrolled or randomised. There can be no exceptions to this rule.

The following steps should be taken in the event that a patient, who does not meet inclusion/exclusion criteria, is found to have been inadvertently randomised in an AstraZeneca study:

- (a) The investigator or monitor should inform the AstraZeneca study team physician immediately. Ensuring patient safety must always be the number one priority
- (b) Study treatment must be discontinued in all cases where continued treatment is deemed to pose a safety risk to the patient. After a discussion between the study team physician and investigator, a decision may be reached that the patient should discontinue study medication. The rationale for discontinuing study medication must be clearly documented. The patient should remain in the study for follow up in accordance with defined study procedures including follow-up on endpoints through the end of the study consistent with the ITT principle

- (c) In those cases where continuation of study therapy is judged not to present a concern related to safety and disease management, the rationale for continuing study therapy must be clearly documented. The patient should continue follow up in accordance with defined study procedures.

5.4 Blinding and procedures for unblinding the study

5.4.1 Methods for ensuring blinding

The treatment allocation in this study will be double blind. Ticagrelor tablets and matching ticagrelor placebo tablets will be provided (see Section 5.5.1), identical in appearance and with the same number, size, and packaging of tablets. Each pack will be labelled with a unique pack ID number that will be used to assign the treatment to the patient but will not indicate treatment allocation to the investigator.

No member of the extended study team at AstraZeneca, the EC, International Steering Committee, or the CEC, personnel at investigational centres or any CRO handling data will have access to the randomisation scheme during the conduct of the study, with the exception of the Supply Chain Study Management department, and the Patient Safety department at AstraZeneca.

A DMC will have access to the individual treatment codes and will be able to merge these with the collected study data while the study is ongoing (see Section 12.4.2). The DMC will review safety data on a periodic basis, including the incidence of AEs, and conduct safety assessments to ensure the ongoing safety of study patients. The DMC responsibilities, authorities, and procedures will be documented in a DMC charter. The personnel involved in the clinical study at AstraZeneca will remain blinded to these analyses and will have no knowledge of the results presented to the DMC.

5.4.2 Methods for unblinding the study

Individual treatment codes, indicating the treatment allocation for each randomised patient, will be available to the investigator(s) or pharmacists from the IVRS/IWRS. Routines for this will be described in the IVRS/IWRS user manual that will be provided to each centre.

The treatment code should not be broken except in medical emergencies when the appropriate management of the patient requires knowledge of the treatment. The AstraZeneca physician or delegate should be consulted whenever possible prior to the investigator breaking the blind. The investigator documents and reports the action to AstraZeneca, without revealing the treatment given to the patient to the AstraZeneca staff. The number of individuals at the study site who become aware of the treatment status should be kept to an absolute minimum including keeping the patient blinded if possible. Treatment with study medication should be continued if considered appropriate.

AstraZeneca retains the right to break the code for SAEs that are unexpected and are suspected to be causally related to a study drug and that potentially require expedited reporting to regulatory authorities. Treatment codes will not be broken for the planned

analyses of data until all decisions on the evaluability of the data from each individual patient have been made and documented.

5.5 Treatments

5.5.1 Identity of study medication(s)

Table 2 Identity of study medication

Study Medication	Dosage form and strength	Manufacturer
Ticagrelor 90 mg	Plain, round, yellow, film-coated tablet, 90 mg	AstraZeneca
Ticagrelor 90 mg placebo	Plain, round, yellow, film-coated tablet, containing zero active therapy (identical in appearance to active)	AstraZeneca
Ticagrelor 60 mg	Plain, round, white, film-coated tablet, 60 mg	AstraZeneca
Ticagrelor 60 mg placebo	Plain, round, white, film-coated tablet, containing zero active therapy (identical in appearance to active)	AstraZeneca

5.5.2 Doses and treatment regimens

At the randomisation visit eligible patients will be randomly assigned to 1 of 2 treatments (see Table 2):

- Ticagrelor 60 mg, one tablet bd given orally
- Ticagrelor 60 mg placebo, one tablet bd given orally

Until the new ticagrelor 60 mg bd study medication with matching placebo is available at the individual study site, ticagrelor 90 mg, one tablet bd given orally, or corresponding placebo, will be used.

Randomisation and treatment pack assignment will be managed via the IVRS/IWRS and the first dose of study medication should be taken as soon as possible after randomisation. Subsequent maintenance doses should be taken morning and evening, at approximately 12-hour intervals, during the treatment period.

Study medication should be swallowed whole with water. Study medication can be taken with or without food. Study medication should not be altered (eg, crushed, put in another vehicle) and should not be given by nasogastric tube or other routes.

5.5.2.1 Dose Switch strategy

When the new study medication comprising of ticagrelor 60 mg or corresponding placebo is locally available at study site, patients already randomized to ticagrelor 90 mg or corresponding placebo will be switched to the new study medication at the next planned visit.

The dose switch must occur on an on-site visit. If the next planned visit is a scheduled telephone contact (e.g. Visit 3, 4, 7, 9, 11, 13 etc.), the patient must be re-scheduled to come in for an on-site visit. By following this strategy all patients at a study site that currently are treated with ticagrelor 90 mg or corresponding placebo, will be switched to the new medication (ticagrelor 60 mg or corresponding placebo) within a 3 months period counted from when the new study medication is available at site.

At the discretion of the PI, an additional visit can be scheduled to allow for a dose switch ahead of next planned visit.

5.5.3 Development of indication for ADP receptor antagonist during study

If a patient randomised to study medication develops an indication for use of an ADP receptor antagonist according to medical guidelines (eg, an ACS or PCI), selection of the appropriate agent for individual patients is at the discretion of the investigator or treating physician and should be made in accordance with local medical guidelines and standard of care.

The patient must temporarily stop study medication during the open-label therapy with the ADP receptor antagonist. Patients should return to randomised treatment (ticagrelor or placebo) when there is no longer an indication for ADP receptor antagonist therapy according to medical guidelines.

5.5.4 Duration of treatment

The study is event-driven and 19000 randomised patients are estimated to be required in order to collect 1385 adjudicated primary endpoint events. The anticipated maximal duration of treatment with study medication for an individual patient is 58 months. However, the actual duration of the study will be based on accrual of the pre-determined number of adjudicated primary endpoint events, and therefore the final treatment time may be shorter or longer than 58 months. The expected minimum follow-up period is 29 months and the expected average follow-up period is 40 months, based on an enrolment period of 28 months. A study closure plan will be developed that accounts for the patient recruitment pattern and the event rate to reach the predetermined number of adjudicated primary endpoint events (1385).

As safety is continuously monitored, the study may be terminated early if either a clear beneficial or harmful effect of the study treatment is detected during the DMC review.

5.5.5 Labelling

Labels will be prepared in accordance with Good Manufacturing Practice (GMP) and local regulatory guidelines. The labels will fulfil GMP Annex 13 requirements for labelling. Label text will be translated into local language.

5.5.6 Storage

All study drugs should be kept in a secure place under appropriate storage conditions and in the original container. The study medication label and the IB specify appropriate storage.

5.6 Concomitant and post-study treatments

5.6.1 Recording of concomitant medication

Detailed recording of **all** concomitant medications (baseline recording) will be made **only** at the randomisation visit (visit 2) and at the study closure visit. Detailed recording of ASA and ADP receptor antagonist use will continue from randomisation throughout the study. In addition, concomitant medication will be recorded in association with SAEs and potential endpoint events from one month prior to start date of the event until one month post start date of the event.

5.6.2 Anti-diabetic treatment and risk factor management

All patients will receive dietary and life-style advice during the study (including recommendation on smoking cessation when applicable), in accordance with local diabetes treatment guidelines. Anti-diabetic medication and medications to treat concomitant risk factors (eg, dyslipidemia and hypertension) should be prescribed, aiming at target levels for glycemic control and risk factor management, according to guidelines.

5.6.3 Oral antiplatelet therapies

Patients requiring antiplatelet therapy other than low-dose ASA will be excluded at study entry.

5.6.3.1 Low Dose ASA (defined as 75 to 150 mg od)

In accordance with national and international clinical practice guidelines, all patients should take open label ASA at a dose of 75 – 150 mg once daily throughout the study, unless contraindicated or not tolerated. The patient will be responsible for the ASA supply throughout the study.

5.6.3.2 High Dose ASA (>150 mg od)

The concomitant use of ASA in any dose >150 mg od during the study is permitted only as a single loading dose, regardless of circumstances (ie, prior MI, ACS, stroke, stent placement of any kind, etc). Long-term maintenance dose of ASA >150 mg od is not permitted in combination with study medication.

5.6.3.3 ADP receptor antagonists

Planned concomitant treatment with any of other ADP receptor antagonists is not allowed in the study. Patients who develop an indication for treatment with an ADP-receptor antagonist during the study may be treated open-label at the discretion of the investigator, as described in Section 5.5.3. Blinded study medication must then be discontinued but should be resumed when open-label treatment with the ADP receptor antagonist is stopped.

5.6.3.4 Dipyridamole

Planned concomitant chronic treatment with dipyridamole is not allowed in the study. If open label treatment with dipyridamole, whether or not in combination with ASA, is considered essential during the study, blinded study medication must be discontinued but should be resumed when open-label treatment with dipyridamole is stopped.

5.6.3.5 Approved PDE3 inhibitors for claudication (eg, cilostazol)

Planned concomitant treatment with any approved PDE3 inhibitor (ie, cilostazol) is not allowed during the study. If open label treatment with a PDE3 inhibitor, whether or not in combination with ASA, is considered essential during the study, blinded study medication must be discontinued but should be resumed when open-label treatment with the PDE3 inhibitor is stopped.

5.6.4 Parenteral antiplatelet therapies

5.6.4.1 GPIIb/IIIa receptor antagonists

Short-term treatment (ie, up to 7 days) with GPIIb/IIIa receptor antagonists is allowed during the study.

5.6.5 Oral anticoagulants

Concomitant treatment with oral anticoagulant drugs (ie, vitamin K antagonists, direct thrombin inhibitors, factor X inhibitors) is not permitted during the study. If treatment with oral anticoagulant drugs is considered essential during the study, study medication must be discontinued, but should be resumed if oral anticoagulant therapy is stopped. Patients should continue to be followed as defined in Section 5.8.1.

5.6.6 Parenteral anticoagulants

Short-term treatment (ie, up to 7 days) with approved parenteral anticoagulants (eg, unfractionated heparin (UFH), low-molecular-weight heparin (LMWH), bivalirudin, fondaparinux) is allowed. However, long-term treatment with LMWH or fondaparinux in outpatients (at venous thrombosis treatment or atrial fibrillation doses) in combination with study medication is not allowed. Concomitant treatment with venous thrombosis prophylaxis doses is allowed. If long-term treatment with parenteral anticoagulant drugs at therapeutic doses is considered essential during the study, study medication must be discontinued, but should be resumed if parenteral anticoagulant therapy is stopped.

5.6.7 Fibrinolytics

Clinical experience with fibrinolytics in combination with ticagrelor is limited at this time and caution should be used. If a patient is to be treated with fibrinolytic therapy, study medication should be stopped and restarted no earlier than 24 hours after completion of fibrinolytic therapy and when the risk of bleeding is deemed low in the judgment of the investigator.

5.6.8 Non-steroidal anti-inflammatory drugs (NSAIDs)

Clinical experience with NSAIDs in combination with ticagrelor is limited at this time. Treatment with NSAIDs is allowed during the study at the investigator's discretion. However, chronic daily dosing with non-selective NSAIDs (eg, patients with rheumatoid arthritis) may increase the potential for gastrointestinal bleeding, so either alternative therapy or concomitant acid suppression therapy is recommended. Treatment with selective cyclooxygenase-2 inhibitors is permitted, although use is cautioned. When pain management is needed, acetaminophen/paracetamol is preferred.

5.6.9 Digoxin and other p-glycoprotein interactions

Ticagrelor modestly increases digoxin levels. Therefore digoxin levels should be monitored closely following initiation of study medication and with any change in study medication. Other p-glycoprotein substrates may be expected to have similar changes in pharmacokinetics. Additional details can be found in the IB.

5.6.10 CYP450 interactions

5.6.10.1 CYP3A4 inhibitors

Strong inhibitors of CYP3A4 enzyme (eg, ketoconazole, itraconazole, voriconazole, telithromycin, clarithromycin [but not erythromycin or azithromycin], nefazadone, ritonavir, saquinavir, nelfinavir, indinavir, atazanavir, or over 1 litre daily of grapefruit juice) should not be co-administered with ticagrelor, as plasma levels of ticagrelor would be substantially increased.

5.6.10.2 CYP3A4 substrates or inducers

Concomitant therapy with simvastatin or lovastatin at doses higher than 40 mg daily is not permitted since administration with ticagrelor will result in higher serum concentrations and may put patients receiving more than 40 mg per day of simvastatin or lovastatin at increased risk of statin-related adverse effects. There are no restrictions to other statin therapies (ie, doses of simvastatin or lovastatin \leq 40 mg daily or any approved dose of any other statin is permitted). Investigators are advised to check lipid levels and adjust statin dosages per local practice and appropriate guidelines. Standard monitoring of patients for possible statin-associated myopathy should be conducted.

Co-administration of ticagrelor with strong inducers of CYP3A4 also should be avoided (eg, rifampin/rifampicin, rifabutin, phenytoin, carbamazepine, phenobarbital, dexamethasone) as plasma levels of ticagrelor could be reduced.

Discontinuation of study medication is up to the judgment of the investigator. If continued antiplatelet medication is judged necessary, there may be a need for extra caution regarding bleeding tendency.

5.6.11 Surgery

It is recommended that cardiac surgery and major non-cardiac surgery that in the opinion of the investigator or treating physician poses a risk for clinically major bleeding should not be performed until at least 5 days after stopping study medication to avoid excessive bleeding. However, local treatment guidelines should be followed. There is a trade-off between stopping study medication too early and risking thrombotic events vs. continuing treatment too close to surgery and risking haemorrhage. Thus it is also recommended that study medication should not be discontinued for significantly longer than 5 days aiming to minimise the risk of thrombotic complications while off study medication.

After surgery, study medications should be restarted when the risk of bleeding is deemed low in the judgment of the investigator or treating physician.

5.6.12 Other surgery and invasive non-cardiovascular procedures

For other surgery or other invasive procedures, study medication may be continued or interrupted temporarily at the discretion of the investigator or treating physician. As with all other surgeries, investigators should collect and record all bleeding events occurring during the surgery or invasive procedures. After the surgery or procedure, study medications should be restarted (if interrupted) as soon as possible.

Other medication, which is considered necessary for the patient's safety and wellbeing, may be given at the discretion of the investigator or treating physician.

5.7 Treatment compliance

The administration of study medication should be recorded in the eCRF. All stops of study medication prescribed by the investigator or treating physician should be recorded. In addition, any non-prescribed temporary stops (>1 week) of study medication should be recorded.

Missed doses of ticagrelor or placebo blinded study medication should not be compensated for (ie, if a dose is missed the next regularly scheduled dose should be taken and should not be doubled).

5.7.1 Accountability

The study medication provided for this study will be used only as directed in the study protocol.

The study personnel will account for all study medication dispensed to and returned from the patient.

Patients will be asked to bring all unused study medication and empty packages to the investigational centre at each on-site visit. The investigator or delegate will enter the amount of returned tablets in the eCRF and make an assessment regarding patient treatment

compliance. Any patient found to be noncompliant would be counselled on the importance of taking their study medication as prescribed.

Any study medication deliberately or accidentally destroyed must be recorded. Any discrepancy between dispensed and returned study medication should be explained.

The investigator will retain the returned medication until the study monitor or delegate collects it, along with any medication not dispensed. The monitor is responsible for confirming the investigator or delegate has recorded the quantities of returned and unused tablets at a patient level before medication is returned to the sponsor and/or destroyed. The study monitor or delegate will advise on the appropriate method for destruction of unused study medication. Destruction of study medication must only be conducted by an authorised centre.

5.8 Discontinuation of study medication

Patients should be discontinued from study medication in the following situations:

5.8.1 Temporary discontinuation from study medication

- Severe thrombocytopenia (platelet count < 50,000/uL). Patients may restart study medication once the severe thrombocytopenia resolves and if considered appropriate by the investigator
- Surgery or procedures associated with major bleeding, see Section [5.6.11](#)
- Major bleeding, see Section [6.4.5.2](#)
- Need of treatment with prohibited concomitant medications, see Section [5.6](#).

For other surgery or other invasive procedures, study medication may be continued or interrupted temporarily at the discretion of the investigator, see Section [5.6.12](#).

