4.2 Exclusion criteria

Patients should not enter the study if any of the following exclusion criteria are fulfilled:

1. Previous MI* (with the exception of definite secondary MI [eg, due to coronary revascularization procedure, profound hypotension, hypertensive emergency, tachycardia, or profound anaemia])
2. Previous stroke (transient ischaemic attack [TIA] is not included in the stroke definition)
3. Planned use of ADP receptor antagonists (eg, clopidogrel, ticlopidine, prasugrel), dipyridamole, or cilostazol. Planned use of ASA treatment at doses >150 mg od
4. Planned coronary, cerebrovascular, or peripheral arterial revascularization
5. Anticipated concomitant oral or intravenous therapy with strong cytochrome P450 3A4 (CYP3A4) inhibitors or CYP3A4 substrates with narrow therapeutic indices that cannot be stopped for the course of the study:
 - Strong inhibitors: ketoconazole, itraconazole, voriconazole, telithromycin, clarithromycin (but not erythromycin or azithromycin), nefazadone, ritonavir, saquinavir, nelfinavir, indinavir, atazanavir
 - CYP3A4 substrates with narrow therapeutic index: quinidine, simvastatin at doses >40 mg daily or lovastatin at doses >40 mg daily
6. Need for chronic oral anticoagulant therapy or chronic low-molecular-weight heparin (at venous thrombosis treatment not prophylaxis doses)
7. Patients with known bleeding diathesis or coagulation disorder, or with uncontrolled hypertension (defined as a systolic BP \geq 180 mmHg and/or diastolic BP \geq 100 mmHg)
8. History of previous intracerebral bleed at any time, gastrointestinal (GI) bleed within the past 6 months prior to randomisation, or major surgery within 30 days prior to randomisation
9. Increased risk of bradycardic events (eg, known sick sinus syndrome, second or third degree AV block or previous documented syncope suspected to be due to bradycardia) unless treated with a pacemaker
10. Known severe liver disease (eg, ascites and/or clinical signs of coagulopathy)
11. Renal failure requiring dialysis

* Previous MI herein refers to a documented hospitalisation with a final diagnosis of spontaneous MI

12. Women of child-bearing potential (ie, those who are not chemically or surgically sterilised or who are not post-menopause) who are not willing to use a medically accepted method of contraception that is considered reliable in the judgment of the investigator OR women who have a positive pregnancy test at enrolment or randomisation OR women who are breast-feeding

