5.8.2 Permanent discontinuation from study medication

- Patient decision: The patient is at any time free to discontinue treatment, without prejudice to further treatment
- Investigator's decision, including but not limited to these examples:
 - Incorrectly randomised patient in whom the inclusion/exclusion criteria violation would put the patient at undue risk
 - AE for which the investigator thinks continued treatment may put the patient at undue risk
 - Severe non-compliance to study protocol
 - Pregnancy.

Each permanent discontinuation from study medication should be communicated to the study team. For decisions around permanent discontinuation the Study Physician can be consulted as appropriate. **NB. Discontinuation of study medication does not mean discontinuation of follow-up or termination of study participation.** Study assessments or telephone follow-up should be continued in all cases if possible, see Sections 5.8.3 and Section 5.9.

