5.8.3.4 Restart of study medication

Whenever possible, restart of randomised study medication should be encouraged, even if a PTDV was previously completed.

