6.4.5.2 Procedures for Study Medication in case of bleeding

Study medication must be stopped immediately in case of a bleed deemed to be clinically significant in the judgment of the investigator (eg, a significant fall in haemoglobin, need for transfusion, haemodynamically significant, or in a critical location such as intracranial, intraspinal, intraocular, or pericardial). Study medication may be resumed when the risk of bleeding is deemed low in the judgment of the investigator. The study medication administration need not be stopped in case of a minor bleeding. All bleedings should be treated and followed up according to local clinical practice. Major bleeding events should be managed according to need with general support and transfusions. It should be noted that platelet transfusion is unlikely to reverse bleeding in a patient receiving ticagrelor, as the new platelets are likely to be inhibited by ticagrelor as long as it is circulating in the blood.

There is no antidote to ticagrelor and treatment of bleedings should therefore be symptomatic and handled according to the clinical routines at the investigational site.

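### A prior intracerebral bleed bars entry for life, yet after an on-study intracerebral bleed blinded drug may be resumed on investigator judgment; the stop should be mandatory and permanent

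*Protocol*

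**What the plan says.** **At entry.** Exclusion 8 in Protocol 4.2 covers "History of previous intracerebral bleed at any time, gastrointestinal (GI) bleed within the past 6 months prior to randomisation". The brain bleed has no time limit; the GI bleed has one. Section 4 allows no exceptions to the criteria.

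**On study.** Among the reasons for temporary discontinuation, Section 5.8.1 lists "major bleeding, see Section" 6.4.5.2. That section is the operative text. It requires an immediate stop for a clinically significant bleed, with examples that include a bleed "in a critical location such as intracranial, intraspinal, intraocular, or pericardial". It then says: "Study medication may be resumed when the risk of bleeding is deemed low in the judgment of the investigator". The intracranial bleed shares this sentence with every other clinically significant bleed.

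**Permanent stop.** The examples in 5.8.2 name no type of bleed. The nearest is an "AE for which the investigator thinks continued treatment may put the patient at undue risk". Consulting the Study Physician is optional.

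**Restart.** Section 5.8.3.4 says that, whenever possible, "restart of randomised study medication should be encouraged, even if a PTDV was previously completed". It carves out no bleed.

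**Prior bleed found after randomisation.** Section 5.3(a) requires immediate notice to the study team physician. Item (b) stops drug where a safety risk is seen, and provides for a discussion between that physician and the investigator. Item (c) lets treatment continue where no such concern is judged to exist, with the rationale documented. None of the three treats exclusion 8 differently from other criteria.

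**The concern.** The wording of exclusion 8 separates a bleed that bars a patient for life from one that bars for six months. On study that separation disappears, and a fresh intracerebral bleed is handled like any other clinically significant bleed. The protocol does not leave a past intracerebral bleed to the investigator's judgment at entry, and gives no reason for doing so after a recent one.

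A survivor of such a bleed could be put back on a blinded drug that may be ticagrelor, usually on top of low-dose ASA. The code is to be broken only in medical emergencies (5.4.2), so the restart decision would normally be made blind. Section 6.4.5.2 itself says: "There is no antidote to ticagrelor and treatment of bleedings should therefore be symptomatic". It adds that platelet transfusion is unlikely to help while the drug is circulating. Section 1.4 reports a minor increase in intracranial haemorrhage of all types over placebo in the earlier long-term ticagrelor trial, with no increase in fatal bleeding. Section 3.2 counts intracranial haemorrhage among irreversible harms.

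**Working it through.** **1. Side by side**

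| Situation | Rule | Who decides |
|---|---|---|
| Intracerebral bleed before entry | Excluded, no time limit (4.2) | Nobody; no exceptions |
| Intracerebral bleed on study | Immediate stop; may resume if risk is deemed low (5.8.1, 6.4.5.2) | Investigator |
| Permanent stop after it | Only if continued treatment is thought to carry undue risk (5.8.2) | Investigator; Study Physician optional |
| Prior bleed found after randomisation | Stop if a safety risk is judged (5.3(b)), otherwise may continue (5.3(c)) | Investigator with study team physician |

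Intracranial in 6.4.5.2 is the broader term and includes intracerebral bleeds, so the resumption sentence applies to them. No row after the first contains a mandatory permanent stop.

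**2. The plan's own figure.** Inputs from Protocol 12.3: HR 0.84, 1385 events, two-sided alpha 4.96% (z = 1.9634), 1:1 allocation. Power = Φ(√1385/2 × |ln 0.84| − 1.9634) = Φ(18.608 × 0.17435 − 1.9634) = Φ(1.2809) = 89.99%, against 90% stated. The same formula solved for events gives 1386, against 1385.

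**3. Bleeds adjudicated as haemorrhagic stroke.** These are primary events (2.1, 6.3.3), and time to the primary event is fixed at the first event (SAP 3.2). Stopping drug afterwards cannot change that patient's contribution, so the primary-analysis cost is zero.

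**4. Other patients.** These have a bleed not adjudicated as stroke (for example, traumatic) or are 5.3 cases. Assumptions:
- The unit is 10 patients, which is not an estimate of how many there will be.
- All 10 are on ticagrelor, as the worst case.
- Each loses 10 to 58 months of drug. The upper end is the anticipated maximum treatment duration; average follow-up is 40 months.
- The log hazard ratio shrinks in proportion to the on-drug time lost.
- The event target stays at 1385.

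The ticagrelor arm has 9500 × 40/12 = 31,667 patient-years. With months lost m, the lost fraction is f = (10 × m/12)/31,667, the diluted HR is exp(ln 0.84 × (1 − f)), and power is recomputed as in step 2.

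| Months lost each | Patient-years lost | f | HR | Power | Loss (points) |
|---|---|---|---|---|---|
| 10 | 8.3 | 0.026% | 0.84004 | 89.97% | 0.02 |
| 20 | 16.7 | 0.053% | 0.84008 | 89.96% | 0.03 |
| 30 | 25.0 | 0.079% | 0.84012 | 89.94% | 0.05 |
| 58 | 48.3 | 0.153% | 0.84022 | 89.90% | 0.09 |

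**5. A harsher check.** Suppose 0.1% to 1% of the ticagrelor arm (9.5 to 95 patients) stopped for good and contributed no treatment effect at all. The HR would be 0.8401 to 0.8415 and power 89.9% to 89.4%. These shares are assumed, not taken from the documents.

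**6. Secondary endpoints.** On-drug time falls by the same 0.03% to 0.15% per 10 ticagrelor patients stopped. Here patients with a haemorrhagic stroke count too, because they remain at risk of later events.

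**The case against.** The strongest reply is that this is a choice between a categorical ban and a risk-based condition. Resumption is permitted, not required, and only when risk is low. If risk stays high after an intracerebral bleed, the present text already withholds drug. The permanent-stop examples in 5.8.2 are not exhaustive and include undue risk. A DMC with access to treatment codes reviews safety, and 5.3 brings wrongly randomised patients before a study team physician. All of this stands, and it is why the point is a gap and not an absence of protection. It does not answer why a bleed that is disqualifying without discretion before entry becomes discretionary when it is recent.

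A second reply is that entry criteria are not stopping rules: prior MI and prior stroke also exclude without a time limit, yet neither forces a permanent stop on study. The parallel is weak. Those exclusions define the study population, whereas exclusion 8 is a bleeding-safety criterion and the on-study bleed is the very hazard it names. It remains true that the protocol does not explain the missing time limit, and that requiring a permanent stop is a clinical judgment, not a computed result.

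A third reply is that the evidence cited in the protocol concerns intracranial haemorrhage of all types, while the change covers only intracerebral bleeds. That is fair. The narrower scope follows exclusion 8, and the evidence is supporting context only.

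A reader might also infer that the protocol contradicts itself, or that 5.8.3.4 pushes sites to restart drug after a brain bleed. The documents support neither. Entry and continuation rules may differ without conflict, and the general encouragement in 5.8.3.4 need not be read as overriding the specific low-risk condition in 6.4.5.2. Its fault is only that it states no exception.

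**Conclusion.** The point holds as a safety gap that should be closed. The protocol bars a past intracerebral bleed absolutely but makes the permanent stop after an on-study one discretionary.

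The size of the harm cannot be stated. Without an intracerebral bleed, restart or re-bleed rate, any count of patients re-exposed or injured would be invented. The power figures show only that the remedy is cheap. They rest on the assumed 10 to 58 months lost and on proportional dilution of the log hazard ratio. The finding concerns the protocol text alone, since the Investigator's Brochure is not available here and may contain restart guidance. The gap gives no ground for doubting the validity of the primary analysis.

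**What to change.** 1. In 5.8.2, list intracerebral haemorrhage diagnosed by the investigator as a mandatory permanent stop of study medication. Say that endpoint follow-up continues in full, consistent with the existing statement there: "Discontinuation of study medication does not mean discontinuation of follow-up or termination of study participation".
2. Except this bleed from the major-bleeding entry in 5.8.1, the resumption sentence in 6.4.5.2 and the restart wording in 5.8.3.4.
3. In 5.3, make item (c) unavailable for a patient found after randomisation to have had a prior intracerebral bleed. Such cases already go to the study team physician, so this is for consistency.
4. Have the sponsor's clinical team set the exact definition, including any exception for microhaemorrhage or haemorrhagic transformation. The stroke definition in 6.3.3 was written for endpoint classification and should not be borrowed as a drug-safety threshold.

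The cost is a few lines of protocol wording and a letter to sites, with no new procedures. Investigators lose discretion for one type of bleed, and a few patients lose on-drug time. Secondary endpoints and the recurrent-event sensitivity analyses in SAP 4.2.1.1 lose a little exposure. The FAS, the follow-up schedule and the 1385-event target do not change.
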